4.2 Exclusion Criteria

Patients are **NOT** eligible for this study if they meet any of the following criteria:

- 1. Patients on ECMO support.
- 2. Patients receiving another inhalation research medication or inhaled nitric oxide.
- 3. Not expected to survive for 48 hours.
- 4. Pregnant (positive pregnancy test in a pre-dose examination) or breastfeeding
- 5. Open tracheostomy.
- 6. Clinical contra-indication, as deemed by the attending physician.
- 7. Allergy to Epoprostenol and its diluent
- 8. Using inhaled vasodilators at baseline.
- 9. Patients who are hemodynamically unstable as determined by investigator

10. Patients with significant hemoptysis as determined by investigator

4.3 Re-Screening of Patients

Patients may not be enrolled more than once.

4.4 Removal of Patients from Therapy or Assessment

Aerogen Pharma or the Investigator may discontinue patients from the study at any time for safety or administrative reasons.

The End of Treatment Study procedures (Day 10) are to be completed for all patients who discontinue from the study prior to Day 10 (except Screen Failure patients).

The Investigator will promptly explain to the patient or their LAR that the study will be discontinued for the patient and provide appropriate medical treatment and other necessary measures for the patient.

Patients who discontinue early from the study will be discontinued for one of these primary reasons: Adverse events, patient death, lost to follow-up, patient withdrew consent, protocol violation, lack of efficacy, investigator decision, study terminated by sponsor, screen failure, or other. Study disposition information will be collected on the Patient Disposition DCF.

4.4.1 Criteria for Stopping VentaProst Treatment

Individual patients stopping criteria: At any time during study drug administration, patients may be removed from study treatment and placed on standard of care (SoC) therapy if they meet one or more of the following pre-defined criteria leading to a deterioration in their condition:

- Severe hypotension as evidenced by a systolic BP < 90 mmHg or MAP < 60 mmHG for >2 hours from the start of VentaProst
- Need for VV ECMO
- Need to increase existing vasopressor therapy by more than 25%
- Worsening oxygenation, ventilatory, or hemodynamic parameters that in the opinion of the investigator the patient should be removed from study treatment
- Massive hemoptysis thought to be clinically significant and not due to endotracheal tube trauma
- Pulmonary Edema

Study stopping criteria: If 3 patients are removed from the study for any of the above conditions, the study will stop further enrollment and investigation will be conducted to determine the cause of the events. An independent safety evaluation will also be conducted. If it is suspected that the investigational product has caused the events, the study will be terminated.

Independent Safety Evaluation: Independent safety evaluation will be conducted by a licensed physician who is not involved in the VentaProst COVID-19 clinical study or the sponsoring organization.

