3.3 Study Design

This is a double-blind, placebo controlled study of VentaProst (Active) as compared to placebo (Control). Active is inhaled epoprostenol administered via the VentaProst delivery system in 10 COVID-19 positive patients. Control is inhaled 0.9% sodium chloride solution administered via the VentaProst delivery system in 10 COVID-19 positive patients. Throughout the remainder of the protocol both Active and Control will be referred to as "study drug". This study will evaluate the potential therapeutic benefit of VentaProst in treating patients with COVID-19 who require mechanical ventilation and are at risk for the progression of respiratory and/ or cardiac/circulatory failure. This study will assess the efficacy and safety of VentaProst at an initial dose of 13.6 ng/kg/min (A range from 3.4-30.6 ng/kg/min may be administered as clinically required for a maximum of 10 days at the discretion of the Investigator. Patients will be followed through Day 28 to assess clinical outcomes.

Patients will be consented and randomized to either the Active or Control group within 48 hours of being placed on mechanical ventilation. Informed consent may be obtained after some screening study procedures were collected as part of the patient's standard of care treatment. Patients will be administered study drug using the VentaProst delivery system which allows up and down titration of study drug to achieve hemodynamic and oxygenation stability. The starting dose of study drug will be initiated at 13.6 ng/kg/min. Based on hemodynamic and oxygenation parameters, the dose of study drug can be increased in 3.4 ng/kg/min increments up to a maximum of 30.6 ng/kg/min or down to a minimum of 3.4 ng/kg/min.

All study staff with the exception of the unblinded pharmacist and Sponsor CRA will be blinded to which treatment regimen a patient has been assigned. Titration and weaning will be performed the same for all patients. Study drug will be administered based on the pump rate calculated for active treatment in mL/hr. Titration guidelines are provided in Section 5.3.3 and Table 3.

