3.4 Duration of Participation

Patients who meet entry criteria will be entered into the study and the duration of study participation for each patient is listed below. The duration of study participation for each patient is as follows:

• Screening: up to 14 days

• Treatment: up to 10 days

• Follow up: 28 days

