7.2 Adverse Events

7.2.1 Definitions

Adverse events are any untoward medical occurrence in a patient administered a pharmaceutical product and which does not necessarily have to have a causal relationship

with this treatment. For the purposes of this study, this will include unanticipated medical events in the judgment of the investigator. *A pre-existing condition* or symptom is one that is present at the start of the study and is reported as part of the patient's medical history. A pre-existing condition or symptom should be reported as an AE only if its frequency, intensity or character worsens during study treatment.

All AEs that occur from the time of the first dose of study medication through the End of Study (Day 28) will be recorded and reported as Treatment-Emergent Adverse Events (TEAE). All AEs must be appropriately documented in the patient's medical chart/source documentation and on the DCFs. When known, investigators should report syndromes rather than list symptoms associated with the syndrome.

All AEs that are ongoing at the conclusion of the study should be followed until: a) resolution/stable sequelae; b) the Investigator determines that it is no longer clinically significant; or, c) the study patient is lost to follow-up. If no follow-up is provided, the Investigator must provide a written justification.

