7.2.2 Adverse Events of Special Interest (AESI)

Pulmonary edema and pulmonary hemorrhage are AEs of special interest due to the mode of action of epoprostenol. If an AE of special interest occurs, the Sponsor will be notified of this occurrence within 24 hours.

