9.1.2.4 Days 2-10 (While on study drug)

- Continue to administer study drug if clinically indicated.
- Adverse Event/SAE assessment daily
- Concomitant medication evaluation daily
- Oxygenation measurement via continuous pulse oximetry (SpO₂)
- Ventilatory parameters assessed twice daily: Ventilator Type, Vent Mode, FiO₂, Inspiratory time, Mean Airway Pressure, Peak Inspiratory Pressure, Positive End Expiratory Pressure, Tidal Volume, and Respiratory Rate
- Vital signs will be assessed twice daily in AM and PM. Efforts will be made to obtain vital signs at the same time each day. Vital signs include: temperature, pulse rate, and blood pressure.
- Time Prone Position-16 hours per day per OSU Protocol

- Chest X-ray (Days 3-8 as clinically indicated)
- Full Chemistry Panel including LFTs, CBC with Diff including neutrophils and lymphocytes, PT/PTT, troponin, and BNP(Days 5 & 10).
- Triglycerides, LDH, ferritin, fibrinogen, CRP, ESR, IL 6 and D-Dimer may be collected if the subject's condition warrants it at Days 5 and Day 10.
- Obtain weight. (Day 10 only or at end of study drug dosing)

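### The study-level safety trigger counts patients who leave the study, although the conditions it refers to only take patients off study treatment

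*Combined protocol and SAP*

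**What the plan says.** The references are to the current version of the protocol, the placebo-controlled one that accepts a molecular or antigen test for COVID-19.

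- **Individual criteria (4.4.1).** For six conditions, such as prolonged hypotension, need for VV ECMO or pulmonary edema, "patients may be removed from study treatment and placed on standard of care (SoC) therapy".
- **Study-level trigger (4.4.1 and synopsis).** "If 3 patients are removed from the study for any of the above conditions", enrollment stops, the cause is investigated and an independent safety evaluation is made.
- **Follow-up (3.3 and 3.4).** "Patients will be followed through Day 28 to assess clinical outcomes". Section 3.4 lists up to 10 days of treatment and, as a separate item, "Follow up: 28 days".
- **Adverse events (7.2.1).** The recording window covers "All AEs that occur from the time of the first dose of study medication through the End of Study (Day 28"), and is not limited to time on drug.
- **Early discontinuation (4.4).** End-of-treatment procedures are required "for all patients who discontinue from the study prior to Day 10", and leaving the study has its own list of reasons on a patient disposition form.

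**The concern.** The trigger points back to the individual criteria but counts a different event. A patient can be off drug and still in the study, and on the literal wording such a patient does not add to the count. This is the only numeric rule in the protocol that pauses enrollment and brings in a physician from outside the study and the sponsor. If whoever keeps the tally takes it from study discontinuations on the disposition form, three patients could come off drug for listed conditions without the pause or the outside review starting. A rule of this kind should have one reading.

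**Working it through.** The plan states no operating characteristics for this rule, so there is no figure to reproduce. The check is a comparison of the text.

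1. **What each condition does.** The opening sentence of 4.4.1 moves the patient from study treatment to standard of care. The criterion on worsening oxygenation, ventilation or hemodynamics names study treatment again. None of the six conditions takes a patient out of the study.

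2. **What the trigger counts.** Both 4.4.1 and the synopsis count removals from the study. No sentence says that this means removal from treatment.

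3. **Whether the two states differ.** They do, in general. Treatment lasts at most 10 days and follow-up runs through Day 28, so a patient dosed for the full 10 days spends 28 − 10 = 18 days off drug and in the study. Dosing may also end sooner: Section 9.1.2.4 has "Obtain weight. (Day 10 only or at end of study drug dosing"). Neither point shows what happens to a patient removed under 4.4.1. They show only that being off drug and still followed is an ordinary state in this design.

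4. **What the literal count does.** Suppose exactly 3 patients are removed from treatment for listed conditions.
   - All 3 also leave the study: the count is 3 and the trigger is met.
   - 1 stays in follow-up: the count is 3 − 1 = 2 and the trigger is not met.
   - All 3 stay in follow-up: the count is 0. If this held for every removed patient, the literal trigger could never be met.
   - The site counts treatment removals, as was probably intended: the count is 3 in every case and nothing is lost.

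5. **Whether a probability can be given.** It would need the rate of treatment removal and the share of removed patients who also leave the study. The documents give neither. Any figure would only restate the assumptions, so none is offered.

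**The case against.** The strongest reply is that context settles the meaning. The rule sits in a section about stopping treatment, and it refers to the conditions just listed, all of which are grounds for stopping treatment. Section 4.4 uses the two terms loosely: it ties end-of-treatment procedures to leaving the study and lists adverse events and lack of efficacy among the reasons for leaving. A site with that habit might record a patient stopped for hypotension as discontinued from the study, and the patient would then count. No sentence says that a patient removed under 4.4.1 stays in follow-up; the Day 28 statements are general.

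The practical risk is also limited. There is one site and about 20 patients. For pulmonary edema and pulmonary hemorrhage, Section 7.2.2 says: "If an AE of special interest occurs, the Sponsor will be notified of this occurrence within 24 hours". Section 7.2.8 sets the same 24-hour limit for SAEs, and Section 11.2.9 lets the sponsor stop the study at any time.

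Most of this stands. It makes treatment removal the likely intent and the consequence modest. It does not make the sentence correct: loose use of the terms in 4.4 is a reason to be exact in the safety rule. Prompt reporting and sponsor discretion also do not replace a pause and outside review that start automatically at a fixed count.

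A reader might infer more than the documents support:

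- **That the rule cannot fire.** This follows only if the wording is applied literally and every removed patient stays in follow-up. The documents establish neither.
- **That safety events would go unseen.** The reporting rules above count against this.
- **That the termination decision cannot work under blinding.** Section 5.5 already gives a route to unblind a patient when necessary. It blinds clinical and research staff and the sponsor, and the independent physician belongs to neither group. At most this is a point of clarification, and no change is proposed.

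**Conclusion.** The concern holds as a wording defect in a stated safety rule. In both 4.4.1 and the synopsis the trigger counts study departures where it should count treatment removals. The consequence is conditional: the pause and the independent evaluation could be delayed or missed if the wording is applied literally and at least one patient needed for the count of 3 remains in follow-up. If the rule is read as probably intended, nothing is lost. How often a literal reading would matter cannot be estimated from the documents. The change should be made because it costs almost nothing and protects the only numeric pause in the plan. Neither the count of 3 nor pooling over arms is in question.

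**What to change.** In 4.4.1 and in the synopsis, replace the words *the study* with *study treatment* in the clause that defines the count. Keep the count of 3, the pooling over both arms and the actions that follow. Add one sentence to 4.4.1 stating that a patient taken off study treatment under these criteria is still followed to Day 28.

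The cost is a few words in two places and one added sentence, made by amendment. The trigger change adds no visits, tests or patients. The follow-up sentence makes explicit what 3.3 and 7.2.1 already say in general terms.

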5. STUDY TREATMENTS

5.1 Identity of Medication Component of the Investigational Product

The study medication VentaProst, Flolan (epoprostenol sodium), is manufactured by GlaxoSmithKline and has been analyzed and released according to their specifications. The labelling of Flolan and placebo for this clinical trial will follow the protocols and procedures set forth by OSU's Investigational Drug Services (IDS). The Control for this study is 0.9% sodium chloride solution, USP from the OSU IDS stock and will be labeled in a blinded manner per the IDS protocols for maintenance of study blind.

Drug Substance Name	Epoprostenol Sodium
Chemical Name	5Z,9α,11α,13 E ,15 S)-6,9-epoxy-11,15-dihydroxyprosta-5,13-dien-1-oic acid.
Molecular Formula	C20H31NaO5
Structural Formula	Na**OOC H H H H OH OH
Molecular Weight	374.45

5.1.1 Storage Condition

Both the vials of study medication and sterile diluent buffer should be stored between 20° to 25°C (68° to 77°F) with excursions permitted to 15° to 30°C (59° to 86°F) and kept in the supplied carton to protect the product from light. Study medication will be stored in a secure, controlled-access location at the study sites.

The 0.9% sodium chloride solution will be stored according the product labelling.

5.2 Treatments Administered

Patients will receive study drug via mechanical ventilator, starting at 13.6 ng/kg/min. If determined by the treating physician, study drug can be up titrated in 3.4 ng/kg/min increments to a maximum of 30.6 ng/kg/min or down to a minimum of 3.4 ng/kg/min. At the Investigator's discretion, the patient will be weaned off the drug in 3.4 ng/kg/min increments. Study drug will be administered based on the pump rate calculated for the active treatment but delivered in mL/hr. Study drug can be administered up to 10 days.

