Study Design	This is a double-blind, placebo controlled study of VentaProst (Active) as compared to placebo (Control). Active is inhaled epoprostenol administered via the VentaProst delivery system in 10 COVID-19 positive patients. Control is inhaled 0.9% sodium chloride solution administered via the VentaProst delivery system in 10 COVID-19 positive patients. Throughout the remainder of the protocol both Active and Control will be referred to as "study drug". This study will evaluate the potential therapeutic benefit of VentaProst in treating patients with COVID-19 who require mechanical ventilation and are at risk for the progression of respiratory and/ or cardiac/circulatory failure. This study will assess the efficacy and safety of VentaProst at an initial dose of 13.6 ng/kg/min (A range from 3.4-30.6 ng/kg/min may be administered as clinically required for a maximum of 10 days at the discretion of the Investigator. Patients will be followed through Day 28 to assess clinical outcomes. Patients will be consented and randomized to either the Active or Control group within 48 hours of being placed on a mechanical ventilator. Patients will be administered study drug using the VentaProst delivery system which allows up and down titration of study drug to achieve hemodynamic and oxygenation stability. The starting dose of study drug will be initiated at 13.6 ng/kg/min. Based on hemodynamic and oxygenation parameters, the dose of study drug can be increased in 3.4 ng/kg/min increments up to a maximum of 30.6 ng/kg/min or down to a minimum of 3.4 ng/kg/min. Study drug will be administered based on the pump rate calculated for active treatment in mL/hr. The titration table below (Table 1) shows the typical up and down titration steps for study drug.

Table 1: Overview of Tit	ration and Weaning Guideline	S
Up titration Guideline*	Downward Titration / Weaning Guideline**	
Start Dose: 13.6 ng/kg/min	Start Dose: 30.6 ng/kg/min	
1 st Step Up Dose (17.0)	1st Step Down dose (23.8)	
2 nd Step Up Dose (20.4)	2nd Step Down Dose (17.0)	
3 rd Step Up Dose (23.8)	3rd Step Down dose (10.2)	
4 th Step Up Dose (27.2)	4 th Step Down dose (3.4)	

5th Step Up Dose (30.6)

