Patients will be weaned from study drug slowly to avoid rebound vasoconstriction. During weaning, doses will be decreased in steps of 6.8 ng/kg/min increments, with a no less than 5 minutes between changes as clinically appropriate. The weaning process should occur in isolation to other treatment changes (no changes in inotropes, vasopressors, or vasodilators) whenever possible. Patients will be observed closely before, during, and after dose changes. In the event patients demonstrate signs of hemodynamic instability or a decrease in oxygenation indicated by pulse oximetry during downward titration, the dose will be returned to its previous level. Once patients have been stable for at least 15 minutes, repeat attempts at dose reduction may be undertaken. The process will continue until patients are fully weaned. Patients will be monitored for safety and efficacy throughout study drug administration.

Number/Type of Patients

Approximately 20 COVID-19 positive patients requiring mechanical ventilation will be enrolled in this study.

Patients will be randomized to either VentaProst Active (aerosolized epoprostenol administered via the VentaProst delivery system) or VentaProst Control (aerosolized 0.9% sodium chloride solution administered via the VentaProst delivery system).

Inclusion Criteria

Patients are eligible for this study if they meet all of the following criteria:

- 1. Women and Men Age ≥18 years old (no upper limit)
- 2. Confirmed COVID-19 positive by a diagnostic test such as molecular or antigen test
- 3. Patients who require invasive mechanical ventilation.
- 4. Enrolled into study within 48 hours of being placed on mechanical ventilation
- 5. Consent or professional consent obtained
- 6. Duration of shortness of breath must be within the previous 14 days.
- 7. Female subjects of childbearing potential must have a negative pre-treatment pregnancy test (serum or urine).
- 8. Received or currently receiving dexamethasone for the treatment of COVID.

^{*} The study drug will be administered based on the pump rate calculated for active treatment in mL/hr.**If the patient has been up-titrated weaning should occur from that level in 6.8 ng/kg/min decrements.

	9. Willing and able to comply with treatment schedule and follow-up.

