Exclusion Criteria	Patients are NOT eligible for this study if they meet any of the following criteria: 1. Patients on ECMO support. 2. Patients receiving another inhalation research medication or inhaled nitric oxide. 3. Not expected to survive for 48 hours. 4. Pregnant (positive pregnancy test in a pre-dose examination) or breastfeeding 5. Open tracheostomy. 6. Clinical contra-indication, as deemed by the attending physician. 7. Allergy to Epoprostenol and its diluent 8. Using inhaled vasodilators at baseline. 9. Patients who are hemodynamically unstable as determined by investigator 10. Patients with significant hemoptysis as determined by investigator
Study Treatment(s)	Patients will receive study drug via mechanical ventilator, starting at 13.6 ng/kg/min. If determined by the treating physician, study drug can be up titrated in 3.4 ng/kg/min increments to a maximum of 30.6 ng/kg/min or down to a minimum of 3.4 ng/kg/min. At the Investigator's discretion, the patient will be weaned off the drug in 6.8 ng/kg/min increments. Study drug will be administered based on the pump rate calculated for active treatment in mL/hr. Study drug can be administered up to 10 days.
Duration of Treatment	The duration of study participation for each patient is as follows: • Screening: up to 14 days • Treatment: up to 10 days • Follow up: 28 days
Criteria for Evaluation	Primary Endpoint 1. Reduction of respiratory failure. Failure is defined by any one of the following: • Requires VV ECMO • Inability to extubate patient within 10 days or reintubation within < 24 hours • Change in S/F, oxygenation index and P/F ratio (≥15%) from baseline to 12 hours, Days 1, 2, 3, 4, 5, 6, 7, 8, 9 and Day 10 (or end of treatment) or
	 Reduction of cardiac or circulatory failure. Failure is defined by any one of the following: Need to begin inotropic therapy or 10% increase in current vasopressor therapy Worsening hemodynamic parameters Cardiac troponin > 20% from baseline BNP ≥ 15% of baseline Need for temporary mechanical circulatory support (IABP, Impella) Requires VA ECMO
	Secondary Endpoints: 1. Improvement in oxygenation defined as any one of the following: • Stabilization of PaO2/FIO2 >250 • Improvement in FIO2 by 50% or improvements ≥15% in S/F, P/F ratio from baseline at 12 hours, Day 5 and Day 10 (or end of treatment)

- 2. Improved clinical outcomes defined as one of more of the following:
 - Shorter time to extubation following the site's extubation protocol

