5.3.3 Study Medication Administration

In the ICU, patients will be started on study drug administered via the VentaProst delivery system at an initial dose administered at 13.6 ng/kg/min. Study Drug Study drug may be titrated up or down in 6.8 ng/kg/min increments (refer to VentaProst Pharmacy Manual) as clinically indicated to a dose range of 3.4 - 30.6 ng/kg/min. Study drug will be administered based on the pump rate calculated for the active treatment in mL/hr. Study drug can be administered up to 10 days.

 $^{^{1}\,\}underline{\text{https://www.accessdata.fda.gov/drugsatfda_docs/label/2018/020444s024lbl.pdf}}$

Table 3: Administration Titration Guidelines*

Up titration Guideline	Downward Titration / Guideline	
Start Dose: 13.6 ng/kg/min	Start Dose: 30.6 ng/kg/min	
1 st Step Up Dose (17.0)	1 st Step Down dose (23.8)	
2 nd Step Up Dose (20.4)	2 nd Step Down Dose (17.0)	
3 rd Step Up Dose (23.8)	3 rd Step Down dose (10.2)	
4 th Step Up Dose (27.2)	4 th Step Down dose (3.4)	
5 th Step Up Dose (30.6)		

^{*}All study drug will be administered per the calculated pump rate for the active treatment in ml/hr

Table 4-Example of Up Titration for male with Ideal Body Weight of 70 kg

Initial Dose Rate	Initial Pump Rate	New Dose Rate	New Pump Rate
13.6 ng/kg/min	1.89 mL/hr	13.6 ng/kg/min	1.89 mL/hr
		17.0 ng/kg/min	2.39 mL/hr
		20.4 ng/kg/min	2.86 mL/hr
		23.8 ng/kg/min	3.33 mL/hr
		27.2 ng/kg/min	3.81 mL/hr
		30.6 ng/kg/min	4.28 mL/hr

Active drug is prepared with 50 mL in each syringe at a concentration of 30,000 ng/mL. All study drug will be administered per the calculated pump rate for the active treatment in ml/hr.

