5.3.4 Study Medication Weaning

Patients will be weaned from study drug slowly to avoid rebound vasoconstriction. During weaning, doses will be decreased in steps of 6.8 ng/kg/min increments, with a no less than 5 minutes between changes as clinically indicated. The weaning process should occur in isolation to other treatment changes (no changes in inotropes, vasopressors, or vasodilators) whenever possible. Patients will be observed closely before, during, and after dose changes. In the event patients demonstrate signs of hemodynamic instability or a decrease in oxygenation indicated by pulse oximetry during downward titration, the dose will be returned to its previous level. Once patients have been stable for at least 15 minutes, repeat attempts at dose reduction may be undertaken. The process will continue until patients are fully weaned. Patients will be monitored for safety and efficacy throughout study drug administration.

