9.1.2.5 Weaning

See Section 5.3.4 and Table 3 for weaning guidelines.

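### Two dosing sentences contradict the rest of the current protocol: Section 5.2 weans in steps of 3.4 ng/kg/min (6.8 elsewhere), and Section 5.3.3 titrates up in steps of 6.8 (3.4 elsewhere)

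*Combined protocol and SAP*

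**What the plan says.** All places cited are in the current version unless stated otherwise.

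**Weaning.** Section 5.2 states that "the patient will be weaned off the drug in 3.4 ng/kg/min increments". Section 5.3.4 states that "doses will be decreased in steps of 6.8 ng/kg/min increments". The synopsis agrees with Section 5.3.4: its weaning paragraph uses 6.8, its Study Treatment(s) row says "the patient will be weaned off the drug in 6.8 ng/kg/min increments", and the Table 1 footnote says "If the patient has been up-titrated weaning should occur from that level in 6.8 ng/kg/min decrements". Section 9.1.2.5 directs the reader elsewhere: "See Section 5.3.4 and Table 3 for weaning guidelines".

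**Up-titration.** Section 5.3.3 states that study drug "may be titrated up or down in 6.8 ng/kg/min increments". Table 3, in the same section, climbs in steps of 3.4, as does the Table 4 pump-rate example. The synopsis (Study Design, Table 1 and Study Treatment(s)) and Sections 2.2.6, 3.3 and 5.2 also use 3.4.

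**Down-titration.** The Table 3 down column, headed "Downward Titration / Guideline", falls in steps of 6.8. So does the down column of Table 1, which the synopsis introduces with "The titration table below (Table 1) shows the typical up and down titration steps for study drug". Section 3.3 sends the reader to Section 5.3.3 and Table 3 for titration. Section 2.2.6 alone clearly gives steps of 3.4 in both directions.

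**The concern.** These sentences tell the bedside team how far to move the dose. Sections 11.2.1 and 11.2.2 require the protocol to be followed as written. Staff cannot wean as both Section 5.2 and Section 5.3.4 instruct, nor follow both the Section 5.3.3 sentence and the up column of Table 3 below it. A monitor could not say which practice is a deviation.

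The Section 5.3.3 sentence carries the more practical risk. It stands in the section that Section 3.3 names for titration, and read literally it doubles the up-step of a drug for which Section 2.2.5 names hypotension as a risk. The stray weaning step in Section 5.2 is the smaller one, so that conflict is mainly a matter of consistency.

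**Working it through.** No sample size, power or error rate is involved. The check is to recover the step from each table, confirm it with the pump rates, and work out what each sentence implies.

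**1. Steps in the tables.**
- Table 3 up column: 13.6, 17.0, 20.4, 23.8, 27.2, 30.6. All five differences are 3.4.
- Table 3 down column: 30.6, 23.8, 17.0, 10.2, 3.4. All four differences are 6.8.
- Table 1 has the same two ladders.

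**2. Reproducing Table 4.** Inputs, all from Section 5.3.3: ideal body weight 70 kg, concentration 30,000 ng/mL. Pump rate in mL/hr = dose × 70 × 60 / 30,000.

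| Dose (ng/kg/min) | Computed | Printed |
|---|---|---|
| 13.6 | 1.904 | 1.89 |
| 17.0 | 2.380 | 2.39 |
| 20.4 | 2.856 | 2.86 |
| 23.8 | 3.332 | 3.33 |
| 27.2 | 3.808 | 3.81 |
| 30.6 | 4.284 | 4.28 |

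The largest gap is at 13.6: 1.89 / 1.904 − 1 = −0.74%. Table 4 is therefore built on up-steps of 3.4.

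**3. Weaning under each sentence.**
- From 13.6 by 3.4 (Section 5.2): 10.2, 6.8, 3.4, off. Four reductions; first cut 3.4 / 13.6 = 25%.
- From 13.6 by 6.8 (Section 5.3.4): 6.8, off. Two reductions; first cut 6.8 / 13.6 = 50%.
- From 30.6: 30.6 / 3.4 = 9 reductions by 3.4. By 6.8 there are five: 23.8, 17.0, 10.2, 3.4, off.
- At 70 kg, the first cut from 13.6 takes the pump from 1.904 to 1.428 mL/hr (10.2 × 70 × 60 / 30,000) or to 0.952 mL/hr (6.8 × 70 × 60 / 30,000).
- At the 5-minute minimum spacing in Section 5.3.4, the time from first change to off, starting at 30.6, is at least (9 − 1) × 5 = 40 minutes against (5 − 1) × 5 = 20 minutes.

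**4. Up-titration under each reading.**
- First step by 3.4 (Table 3): 13.6 to 17.0, which is 3.4 / 13.6 = +25%, at 2.380 mL/hr.
- First step by 6.8 (literal Section 5.3.3 sentence): 13.6 to 20.4, which is 6.8 / 13.6 = +50%, at 2.856 mL/hr.

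**5. Which value is intended.** For weaning, Section 9.1.2.5 points to Section 5.3.4 and Table 3, and both give 6.8, so Section 5.2 is the outlier. For up-titration, the Section 5.3.3 sentence stands alone against three tables and five other places. The preceding version in the combined document used 3.4 in all three of these sections, which suggests a missed edit in Section 5.2 and the new weaning step carried too far in Section 5.3.3. That is an inference about origin only; the conflict lies wholly within current text.

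**The case against.** The strongest case against is that these are copy-editing slips whose resolution is already on the page. Much of it stands. Tables 3 and 4 sit directly below the Section 5.3.3 sentence and make up-steps of 3.4 the likely practice. That sentence also refers to the Pharmacy Manual, which was not available here and may settle bedside use. No misdosing is shown.

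The safety weight is modest as well. The 30.6 ceiling is the same under either step. The current version sets no minimum interval between up-steps, so two steps of 3.4 can reach 20.4 quickly within protocol. A reader might see 20.4 as alarming because it was the top dose given in the sponsor's earlier Phase 2a study (Section 2.2.4). But Section 2.2.6 says doses up to 30.6 were approved for that study, and Table 3 here lists 20.4 as the routine second step. Section 2.2.3 gives a half-life generally under 3 minutes after an intravenous bolus, and Section 4.4.1 has a hypotension stopping criterion.

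Two stronger readings are tempting and do not hold:
- **That the down-titration step is unsettled throughout the protocol.** Section 3.3 sends titration to Section 5.3.3 and Table 3, and for downward moves these agree on 6.8. The synopsis and Sections 3.3 and 5.2 attach 3.4 to the increase and then state only a floor. Section 2.2.6, a rationale section, is the one clear exception.
- **That steps of 6.8 are impossible because from 13.6 they give 20.4, 27.2, 34.0 upward and 6.8, 0 downward, missing 30.6 and 3.4.** Those figures bound a permitted range and need not be rungs of the ladder.

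What remains is that two operative sentences state the wrong step, and a protocol should not rely on a separate manual to override its own text.

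**Conclusion.** The point holds for two sentences. Section 5.2 gives the wrong weaning step (3.4, should be 6.8), and Section 5.3.3 gives the wrong up-titration step (6.8, should be 3.4). Each changes the first move from 13.6 by a factor of two. Section 2.2.6 needs a minor consequential edit.

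This should be fixed because the sentences are operative and the correction is nearly free. The benefit is consistent dosing with a modest safety gain. A reader might infer a threat to the treatment comparison, but the documents do not support it: clinical and research staff are blinded (Section 5.5), titration and weaning follow the same rules in both arms, and control is pumped at the rate calculated for active drug (Section 3.3). No statistical figure depends on the step.

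The verdict assumes that the tables and the cross-references in Sections 3.3 and 9.1.2.5 express the sponsor's intent. The Pharmacy Manual could not be checked.

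**What to change.** 1. In Section 5.2, change the weaning step from 3.4 to 6.8 ng/kg/min.
2. In the Section 5.3.3 sentence, change the up-titration step from 6.8 to 3.4 ng/kg/min, leaving 6.8 for downward moves.
3. In Section 2.2.6, align the downward step with 6.8. If the sponsor instead intends 3.4 for lowering the dose outside weaning, say so in Section 5.3.3 and Table 3.
4. Check that the Pharmacy Manual gives the same steps.

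The cost is one sentence in each of the three sections, or a clarification in Section 5.3.3 and Table 3 if the sponsor takes the alternative in item 3, plus the manual check. Sample size, data collection and analysis are unaffected.
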